Variables and measurements

The primary outcome is all-cause mortality assessed at 28 days from the recruitment of the patient.

Moreover, at the descriptive level and in order to check the homogeneity of both groups, the following variables will be collected at the time of recruitment: birth year, gender, height, dry weight, body temperature, heart rate, blood pressure, count blood cell, glucose level, plasma creatinine, bilirubinaemia, plasma C reactive protein, procalcitonin level, blood gas analysis, lactate, urinary output(mL/kg/hours), arterial oxygen tension/fractional inspired oxygen ratio, International Normalized Ratio(INR),Prothrombin time(second),activated partial thromboplastin time(second),Fibrinogen(g/L),D-Dimer(mg/L),Organ function(Acute Physiology and Chronic Health Evaluation II, Sequential Organ Failure Assessment, The Confusion Assessment Method for The Intensive Care Unit).

Secondary Outcome: all-cause mortality within 90 days from randomization ,free hours of vasoactive drugs after randomization within 14 days.

Finally, for all patients enrolled in the study, 10 ml of whole blood was taken from 8 am to 10 am every day, After centrifugation, the plasma was stored in a negative 80-degree refrigerator for subsequent follow-up testing.

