## Statistical Analysis Plan

Patients will be divided into control or intervention with center randomisation. Full Analysis Set (FAS): Analyzes all cases that were randomized into clinical trials. The shed data was estimated using the LOCF method. Per Protocol Set(PPS): Analysis of all cases that meet the test plan, good compliance, no banned drug use during the trial, and complete the contents of the CRF regulations. The efficacy analysis of this trial was simultaneously analyzed using the full analysis set and the compliance set. The entire analysis will be undertaken with “the intention-to-treat” principle, even though we have foreseen a “by protocol” analysis. only patients who have received at least the minimum established doses of PEA treatment in the experimental arm will be evaluated.

The descriptive analysis will be performed using means and SDs for quantitative variables and absolute and relative frequencies for qualitative variables. To verify the homogeneity of both groups,  $\chi^2$  (Pearson or Fisher) and t-test will be used. To determine the benefit of our intervention, the clinical relevance indicators will be calculated: relative risk, absolute risk reduction, relative risk reduction, number needed to treat.

Specific analysis method:

1. Statistical descriptions were performed for the cases of rejection and shedding and for pretreatment data, Pearson  $\chi^2$  test was used for all-cause mortality within 28 and 90 days.
  2. Pearson  $\chi^2$  test or exact probability calculation, t-test or analysis of variance and non-parametric test were performed for other outcomes.
  3. the central effect CMH method was performed for the comparison of the clinical efficacy of the two groups, and the qualitative or ordinal variables are analyzed by using the GEE method.
  4. A statistical description method was used for adverse reactions. Chi-square or Fisher exact test were used for the incidence of adverse reactions between groups.
  5. Survival analysis: Cox survival curve; multivariate analysis: unconditional logistic regression;
- All analyses will be performed with a significance of 5% and the associated CI of each relevant parameter will be calculated. The statistical software used will be IBM SPSS Statistics V.22.

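### 28-day mortality is tested with a valid but unadjusted chi-square; prespecified adjustment for baseline APACHE II would add power, and the other mortality analyses need a rank

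*SAP*

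**What the plan says.** The primary outcome is death from any cause at 28 days (Protocol, Variables and measurements). In the SAP's list of specific analysis methods, item 1 says a Pearson chi-square "test was used for all-cause mortality within 28 and 90 days". No covariate is named.

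Two other items could bear on the same endpoint. Item 3 says "the central effect CMH method was performed for the comparison of the clinical efficacy of the two groups". Item 5 lists a Cox survival curve and "multivariate analysis: unconditional logistic regression", with no outcome or covariates. Nothing ranks items 3 and 5 against item 1.

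The Protocol collects baseline variables at recruitment, including "Organ function(Acute Physiology and Chronic Health Evaluation II, Sequential Organ Failure Assessment". Their stated purpose is "at the descriptive level and in order to check the homogeneity of both groups". The Methods section says recruitment ends with randomisation, so APACHE II can serve as a baseline covariate, but it has no stated role in the efficacy analysis.

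Three other SAP statements bear on the remedy: "the clinical relevance indicators will be calculated: relative risk, absolute risk reduction, relative risk reduction, number needed to treat"; "The shed data was estimated using the LOCF method"; and "The statistical software used will be IBM SPSS Statistics V.22".

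**The concern.** If severity at entry predicts death, an analysis that conditions on it detects the same treatment effect with fewer patients. The plan collects the score and lists a logistic model, but does not connect the two for the primary endpoint.

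Ranking is a second, smaller matter. The chi-square and an adjusted test sometimes reach different verdicts on the same data. If items 3 and 5 are not labelled supportive, a reader cannot confirm from the plan that the analysis reported as decisive was the one intended. Type I error rises only if item 1 is disregarded as the primary test and the most favourable result is reported.

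**Working it through.** **Inputs from the Protocol's sample-size paragraph and table.** Control risk 0.40, odds ratio 0.36, target alpha 0.0250 (table), 76 per arm, stated power 0.8041, final total 168 (84 per arm).

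**Reproducing the planned figure.**

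- Treatment risk: the odds are 0.36 × 0.40/0.60 = 0.24, so p1 = 0.24/1.24 = 0.1935, as in the table.
- Pooled-variance formula: n = [1.960 √(2 p̄(1 − p̄)) + 0.842 √(p1(1 − p1) + p2(1 − p2))]² / (p2 − p1)², with p̄ = 0.2968.
- The numerator is (1.960 × 0.6461 + 0.842 × 0.6294)² ≈ 3.225 and the denominator is 0.2065² ≈ 0.0426. This gives 75.7, so 76 per arm.
- Exact enumeration of the chi-square gives power 0.8041 with p1 unrounded (0.8043 with p1 = 0.1935). The plan's figure is confirmed.
- At 84 per arm, if all 168 patients are in the full analysis set, exact power is 0.8462.
- Exact null rates are 0.0492 and 0.0536 at 76 per arm and 0.0513 and 0.0497 at 84 (common risk 0.297 and 0.40). The test is sound.

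**Gain from adjustment.** The documents give neither the AUC of APACHE II nor the number of centres, so both are assumed. The simulation used 20,000 trials per scenario and six equal centres with SD 0.3 on the logit scale (0 for the useless score). The model contained treatment and score only, with a Wald test at two-sided 5%. Gains were taken before rounding.

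| Assumed AUC | 76 per arm: chi-square / adjusted | Gain (points) | 84 per arm: chi-square / adjusted | Gain (points) | Chi-square size per arm to match 84 adjusted |
|---|---|---|---|---|---|
| 0.50 (useless) | 0.805 / 0.801 | −0.4 | 0.847 / 0.840 | −0.7 | – |
| 0.635 | 0.802 / 0.818 | +1.6 | 0.848 / 0.856 | +0.8 | 87 |
| 0.68 | 0.807 / 0.834 | +2.7 | 0.844 / 0.869 | +2.4 | 91 |
| 0.72 | 0.810 / 0.853 | +4.3 | 0.848 / 0.884 | +3.6 | 95 |
| 0.756 | 0.802 / 0.871 | +6.8 | 0.843 / 0.898 | +5.5 | 99 |

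The last column uses exact chi-square power: 0.8587 at 87, 0.8717 at 91, 0.8848 at 95 and 0.8992 at 99. The extra patients in total are 2 × (87 − 84) = 6, then 14, 22 and 30. Monte Carlo standard error is about 0.003 for power and 0.002 for the paired gain.

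A separate simulation with a likelihood-ratio test and no centre effect agrees. At 76 per arm, power was 0.807 against 0.820 at AUC 0.60, 0.809 against 0.853 at 0.70, and 0.807 against 0.905 at 0.80.

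**Type I error.** Under the null the Wald test rejects in 4.8–5.1% of trials and the chi-square in 4.8–5.4%. A second simulation used permuted blocks of 4 within 6 or 12 unequal centres, centre SD 0.3 or 0.6, AUC 0.68 and 84 per arm. With centre left out of the model, the Wald null rate was 4.5–4.9% and the gain 2.0–2.7 points, so omitting centre does not inflate error. CMH by centre alone adds no power (0.79–0.80 at 76 per arm, 0.83–0.84 at 84).

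**Ranking.** When severity is prognostic, the chi-square and the adjusted test disagree in 3.7–9.8% of trials under the planned effect and 2.7–4.0% under the null. Declaring success if any of chi-square, CMH or Wald logistic is significant gives a null rate of 6.2–7.8% if severity is prognostic and 5.9–6.2% if not. That is 1.5–2.7 and 0.8–1.2 points above the chi-square's own rate.

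**Missing scores.** With missing scores replaced by the overall mean at 84 per arm, power falls by 0.2 points at 5% missing and 0.3–1.0 points at 10%. The null rate stays at 4.8–5.6%.

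**The case against.** There is no defect to correct. Item 1 applies to the primary outcome the very test the trial was sized for, and at 84 per arm that test already has 84.6% power. The gain rests on an assumed AUC and could be slightly negative. Nothing in the documents favours APACHE II over SOFA or lactate, which are also collected. Item 1 is the only item that names 28-day mortality, so on an ordinary reading it governs. Two valid tests that sometimes disagree do not by themselves inflate error. Item 5 already plans a logistic model.

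The remedy can be criticised too. A Wald test on a conditional odds ratio sits on a different scale from the promised risk-based measures. A likelihood-ratio test is about 0.5–0.9 points more powerful than Wald and loses nothing at 76 per arm with a useless score (0.807 against 0.810).

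Most of this stands as a limit on the claim: the point is efficiency, the gain depends on the score, and error inflation requires item 1 to be set aside. The choice of score is a judgement; what matters is naming it in advance. A prespecified likelihood-ratio test would be a reasonable alternative to Wald. None of this makes adjustment unsound, and item 5 as written is not a prespecified adjusted analysis because it names no outcome, covariates or rank.

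**Conclusion.** The point holds as a worthwhile improvement, not an error. The chi-square is valid and delivers its planned power. Adjusting for APACHE II would add 0.8 to 5.5 points at 84 per arm, or 1.6 to 6.8 at 76, if its AUC lies between 0.635 and 0.756. If the score carries no information, the loss is 0.4–0.7 points. These figures rest on the planned risks of 40% and 19.35%, the assumed AUCs and the assumed centre structure. The 84-per-arm figures also require all 168 patients to be in the full analysis set. Separately, the missing rank of items 3 and 5 should be settled whichever test is primary.

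**What to change.** Before any comparison of outcomes by arm, amend the SAP as follows.

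- **Primary analysis:** 28-day death in the full analysis set, by logistic regression on treatment and continuous baseline APACHE II only, with a Wald test at two-sided 5%. This matches the table's 0.0250 per side; the text's one-sided 0.05 should be reconciled with it. Naming the full analysis set also settles its rank against the per-protocol set, which the SAP now analyses alongside it.
- **Centre:** leave it out of this model; item 3's CMH covers it as a sensitivity analysis.
- **Missing APACHE II:** replace by the mean of both arms combined. The LOCF rule for missing outcome status is not changed by this proposal.
- **Reporting:** relative risk, absolute risk reduction and number needed to treat, with 95% intervals, by standardising the model; the Wald test is the decision rule. State that the adjusted odds ratio is conditional and not comparable with the planned marginal 0.36.
- **Other analyses:** use the same model at 90 days, and label the chi-square, CMH and Cox analyses as sensitivity analyses.

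Minimum version, if the chi-square is kept as primary: say so, name APACHE II as the covariate in item 5's logistic model, and label items 3 and 5 supportive.

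**Cost.** No new data are needed. Beyond the small power loss if the score is uninformative, there are three costs:

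- Standardisation may need software beyond SPSS V.22.
- The Wald test and the standardised intervals can disagree under the planned effect: in 0.8–1.1% of trials for the absolute risk reduction and 0.4–0.9% for the relative risk. The delta-method interval for the absolute risk reduction, used alone, has a null rate of 5.2–5.7% without centre stratification.
- The conditional odds ratio, about 0.33 to 0.28 over the assumed AUCs, must be explained against 0.36.

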Study Protocol

Efficacy of Therapeutic Plasma Exchange Adsorption Diafiltration(PEAF)
for Septic Shock With Multiple Organ Dysfunction Syndrome in intensive care unit:
A Multicenter,Open-Parallelled ,Randomized and Controlled Clinical Trial

Original Protocol : May 18,2018

Principal Investigator

[name] MD PhD

Sponsor

Shenzhen Second People's Hospital

Investigators and Institutional Review Board

Principal Investigator

[name] MD PhD

Other Investigators

School of Public Health, Southern Medical University

[name]

[name]

Institutional Review Board

The IRB

Background

Septic shock with multiple organ dysfunction syndrome (MODS) is a life-threatening clinical condition due to coagulant disorder immunoparalysis to infection. For this reason the extracorporeal therapies for the treatment of septic shock with MODS have become widespread in the ICU and, at the same time, new extracorporeal depurative techniques have been developed for the removal of inflammatory mediators. One of these techniques is therapeutic plasma exchange (TPE) that remove pathologically elevated cytokines and simultaneously to replace protective plasmatic factors. other techniques is CPFA (coupled plasma-filtration adsorption) that uses a sorbent once the separation between plasma and blood has been obtained with a plasma filter. The others is Plasma dialysis filtration(PDF) that can remove inflammatory mediators for patients with multiple organ dysfunction syndrome.

Aims and Goals

The current protocol is to evaluate the effect of Therapeutic Plasma Exchange Adsorption Diafiltration (PEAF) on Septic shock with multiple organ dysfunction syndrome (MODS).

Setting and design

This is a open-parallelled ,randomized and controlled clinical trial and the study is endorsed by Health and Family Planning Commission of Shenzhen Municipality and Shenzhen Second People's Hospital, and is approved by Medical ethics committee of Shenzhen No.2 People's Hospital.

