According to the mortality rate of patients with sepsis combined with MODS in our hospital for about one year is about 40%. The literature reported that the OR of coupled plasma-filtration adsorption(CPFA)treatment group was 0.36 (according to $\alpha=0.05$, unilateral, $1-\beta=0.8$; $n=152(76\times 2)$), according to statistical principles, The sample size calculated by PASS11.0 requires at least 152 cases, an increase of 10% of shedding cases. the total number of cases is at least 168 subjects finally.

	Sample Size Grp 1	Sample Size Grp 2	Prop H1 Grp 1 or Trtmnt P1	Prop Grp 2 or Control P2	O.R. if H0 OR0	O.R. if H1 OR1	Target Alpha	Actual Alpha	Beta
Power	N1	N2	P1	P2	OR0	OR1	Alpha	Alpha	Beta
0.8041	76	76	0.1935	0.4000	1.000	0.360	0.0250	0.0259	0.1959

Methods:

The patients are considered registered once the informed consent form has been obtained by the patient or legal representative. The recruitment process ends with the patient center randomisation. Patients will be divided randomly into two arms (control and intervention).

The characteristics of the groups are: Control group: Treatment following the suggestions provided by the recent surviving sepsis guidelines, as well as standard care guidelines typically followed in China. HVHF, High volume hemofiltration for septic shock with MODS is permitted in Control group routinely (Blood pump: 200ml/min, replacement fluid pump 45ml/kg/min, dialysate pump 45ml/kg/min, waste pump 90ml/kg/min, and high-volume hemofiltration for 16 hours with ACF180™ AsahiKASEI or AV1000S™ Fresenius)

Intervention group: the patient is placed in the PEAF group, he/she will receive treatment with PEAF immediately after randomization. PEAF that is TPE (therapeutic plasma exchange 20ml/kg/d Fresh frozen plasma, Blood pump: 120ml/min, replacement pump 20ml/kg/min, dialysate pump 0ml/kg/min, waste pump 20ml/kg/min, plasma exchange 1 hour) plus PFA (Blood pump: 120ml/min, Plasma separation rate 25-30%, plasma-filtration adsorption with Mediasorb™ BELLECO ITALY

≥30ml/min) and HVPDF(High volume plasma diafiltration with ACF180™ AsahiKASEI or Ultraflux AV1000S™ Fresenius , Blood pump same as PFA , replacement fluid pump 2000ml/h, dialysate pump 2000ml/h, waste pump 4000ml/h),with PFA and HVPDF for 15 hours in the first 3 days. Same protocol with control group after 3days.

The scheme of the trial is displayed in figure 1 and figure 2

[figure not shown]

Figure 1: Study diagram

[figure not shown]

Figure 2: Pipeline connection

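### The only between-arm safety test counts adverse reactions, with no causality rule, assessor or window, in an open trial, so the non-fatal comparison is open to differential attribution

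*SAP*

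**What the plan says.** Safety appears only in item 4 of Specific analysis method in the SAP. It has two sentences: "A statistical description method was used for adverse reactions", and then "Chi-square or Fisher exact test were used for the incidence of adverse reactions between groups". Neither says what counts as a reaction, who decides, or over what period. The SAP sets a 5% significance level for all analyses.

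The Protocol, under Setting and design, states: "This is a open-parallelled ,randomized and controlled clinical trial". No blinded assessor or adjudication is described.

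Under Methods, PEAF patients receive plasma exchange with fresh frozen plasma, sorbent adsorption and diafiltration for the first three days, then follow the control protocol. Controls receive guideline care, and "HVHF, High volume hemofiltration for septic shock with MODS is permitted in Control group routinely". The documents do not say how many controls will receive it.

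Under Variables and measurements, blood count, coagulation and organ-function items fall under the statement that "the following variables will be collected at the time of recruitment". What is collected after that is:

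- "The primary outcome is all-cause mortality assessed at 28 days from the recruitment of the patient".
- "Secondary Outcome: all-cause mortality within 90 days from randomization ,free hours of vasoactive drugs after randomization within 14 days".
- Daily blood, from which "the plasma was stored in a negative 80-degree refrigerator for subsequent follow-up testing". No safety assay is named.

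No adverse-event or adverse-reaction variable is listed. The SAP mentions a CRF, but its contents are not given.

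**The concern.** In its ordinary sense an adverse reaction is an event plus a judgement that treatment caused it. In septic shock with organ failure, a bleed, a platelet fall or a new infection can come from the disease or from an extracorporeal circuit, so that judgement is seldom clear-cut. In an open trial, whoever makes it may know the arm. Because the arms also differ in procedure exposure, the share of events called reactions can differ between them even when the events occur equally often.

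The bias can go either way. PEAF events may be attributed readily because the procedure is new and visible, which creates apparent harm. They may instead be put down to the underlying shock, which hides real harm. Item 4 is the only planned safety test of a combined extracorporeal procedure, so what is at stake is the non-fatal safety conclusion. The primary mortality analysis is not affected.

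**Working it through.** **The plan's own figure.** No event rate or power is stated for safety. The only design figure is the sample size for mortality, which supplies the number per arm used below. With control mortality P2 = 0.40 and OR = 0.36:

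- Odds under PEAF = 0.36 × 0.40/0.60 = 0.24, so P1 = 0.24/1.24 = 0.1935, as tabulated.
- At the table's target alpha of 0.0250 (one-sided), the pooled-variance formula gives 76 per arm. Exact enumeration at 76 per arm gives power 0.8041, equal to the table.

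**Inputs to the illustration.** From the documents: n = 76 per arm and a two-sided 5% test. Assumed, because the documents give neither: the true any-cause event rate q and the share of events called reactions, a1 (PEAF) and a0 (control).

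**Formulas.** Observed reaction incidence = q × a in each arm. With x1 and x0 reactions, the Pearson statistic is z = [(x1 − x0)/n] / √[p̄(1 − p̄) × 2/n], where p̄ = (x1 + x0)/(2n). The rejection probability is the sum of the binomial probabilities of all (x1, x0) with |z| > 1.96.

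**No true difference between arms.** At q = 40%, attribution of 60% v 40% compares 0.40 × 0.60 = 24% with 0.40 × 0.40 = 16%. Attribution of 70% v 30% compares 28% with 12%.

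| True rate, both arms | 50% v 50% attributed | 60% v 40% | 70% v 30% |
|---|---|---|---|
| 20% | 5.1% | 13.1% | 38.4% |
| 40% | 5.1% | 23.6% | 71.0% |
| 60% | 4.9% | 36.3% | 90.7% |

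At 84 per arm (168/2), the 40% row gives 5.1%, 25.8% and 75.4%. Fisher's test, which item 4 also allows, is more conservative and would reject somewhat less often.

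**True excess under PEAF, 40% v 20%.**

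| Events counted | Rates compared | Probability of rejection |
|---|---|---|
| All | 40% v 20% | 77% |
| 50% attributed in each arm | 20% v 10% | 42% |
| 40% (PEAF) v 60% (control) attributed | 16% v 12% | 11% |

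Equal attribution keeps the error rate near 5% but costs power. Unequal attribution can create a difference or hide one. A more extreme gap can reverse the direction: with true rates of 42% v 30% and attribution of 10% v 50%, the rates compared are 4.2% v 15%, the pooled rate is 9.6%, and z = −0.108/√(0.096 × 0.904 × 2/76) = −2.26, an apparent benefit.

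**The case against.** The strongest reply is that the causal reading is brought in from outside. The SAP never says that causality is judged, by whom, or that only study-procedure events count. Its English is loose throughout, and adverse reactions may simply mean adverse events. That is possible, and it limits what can be claimed. The text does not say so, however, and the same change to item 4 would settle it.

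Three stronger readings are tempting, and the documents do not support them.

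- A reader might infer that controls score zero by definition because they have no study procedure to react to. Haemofiltration is permitted routinely in controls, with filters, flows and duration specified, and guideline care can itself cause reactions. Exposure differs between arms, but it is not absent in controls.
- A reader might infer that no follow-up safety information is collected. All-cause mortality at 28 and 90 days is collected and compared, and it captures fatal harm without attribution. Plasma is stored daily, and the CRF may record more than is shown. What is missing from the documents is a listed non-fatal safety variable.
- A reader might infer that the comparison measures attribution instead of harm. Bias arises only if attribution differs between arms, and nothing in the documents shows how far it would.

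It is also fair to say that safety is not a named outcome and that every rate in the illustration is assumed. Both points stand. They limit the weight of the point, but mortality does not replace a non-fatal safety comparison.

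**Conclusion.** The point holds in a limited form. Item 4 tests an undefined reaction count in an open trial whose arms differ in procedure exposure, with no causality rule, assessor, window or listed non-fatal follow-up variable. On the term's ordinary meaning, the result is open to differential attribution in either direction, and a significant or null finding could not be read with confidence.

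The size cannot be derived from the documents. Over the assumed range (true rates of 20% to 60%, attribution of 60% v 40% to 70% v 30%, 76 per arm), a nominal 5% test rejects between 13% and 91% of the time with no true difference. With equal attribution it stays near 5%. The conclusion rests on two assumptions: that reaction carries its usual causal sense, and that the CRF contains no rule that would remove the problem. It should be put right, but it does not touch the primary endpoint.

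**What to change.** Change item 4 to compare all adverse events regardless of attribution, counted from randomisation over the same fixed window in both arms. Use one common list of events that can occur in either arm, for example bleeding, new infection, and falls in platelets or fibrinogen defined from routine laboratory values. Add the list, its definitions and the window to Variables and measurements.

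Report deaths in the window alongside, or treat death as a competing event. At the planning rates, 76 per arm implies about 0.1935 × 76 = 14.7 deaths under PEAF and 0.40 × 76 = 30.4 in controls by day 28, so time at risk would differ between arms.

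Keep circuit or catheter complications and transfusion reactions off the tested list, because they depend on exposure or need a causal call. Report these and investigator-judged reactions descriptively, with the number of patients exposed in each arm.

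The cost is a revised SAP item and one added CRF page. Event counts will rise in both arms because sepsis-related events are included. Recording would still be unblinded, so the laboratory-defined events will be the least open to judgement. Treatment, sample size and the primary analysis are unchanged.
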